8.2.4. Clinical Safety Laboratory Tests

- See Appendix 2 for the list of clinical laboratory tests to be performed and the SoA for the timing and frequency.
- The investigator must review the laboratory results, document this review, and report any clinically relevant changes occurring during the study as an AE. The laboratory results must be retained with source documents unless a Source Document Agreement or comparable document cites an electronic location that accommodates the expected retention duration. Clinically significant abnormal laboratory findings are those that are not associated with the underlying disease, unless judged by the investigator to be more severe than expected for the participant's condition.
- All laboratory tests with values considered to be clinically significantly abnormal during participation in the study or within 2 weeks after the last dose of study intervention should be repeated until the values return to normal or baseline or are no longer considered clinically significant by the investigator or medical monitor.
 - If such values do not return to normal or baseline within a period judged reasonable by the investigator, the etiology should be identified, and the Sponsor should be notified.
 - All protocol-required laboratory assessments, as defined in Appendix 2, must be conducted in accordance with the SoA, standard collection requirements, and laboratory manual.
- If laboratory values from non-protocol specified laboratory assessments performed at an investigator-designated local laboratory require a change in participant management or are considered clinically significant by the investigator (for example, SAE, AE, or dose modification), then report the information as an AE.

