8.2.5. Hepatic Monitoring

Close hepatic monitoring

Initiating laboratory and clinical monitoring for abnormal liver laboratory test results

Laboratory tests (Section 10.5), including ALT, AST, ALP, TBL, direct bilirubin, gamma-glutamyl transferase, and creatine kinase, should be repeated within 48 to 72 hours to confirm the abnormality and to determine if it is increasing or decreasing, if 1 or more of these conditions occur.

If a participant with baseline results of	develops the following elevations:
ALT or AST $<1.5 \times$ ULN	ALT or AST $\geq 3 \times$ ULN
ALP $<1.5 \times$ ULN	ALP $\geq 2 \times$ ULN
TBL $<1.5 \times$ ULN	TBL $\geq 2 \times$ ULN (except for participants with Gilbert's syndrome)
ALT or AST $\geq 1.5 \times$ ULN	ALT or AST $\geq 2 \times$ baseline
ALP $\geq 1.5 \times$ ULN	ALP $\geq 2 \times$ baseline
TBL $\geq 1.5 \times$ ULN	TBL $\geq 1.5 \times$ baseline (except for participants with Gilbert's syndrome)

Abbreviations: ALP = alkaline phosphatase; ALT = alanine aminotransferase; AST = aspartate aminotransferase; TBL = total bilirubin; ULN = upper limit of normal.

What to do if the abnormal condition persists or worsens

If the abnormality persists or worsens, clinical and laboratory monitoring and evaluation for the possible causes of abnormal liver tests should be initiated by the investigator in consultation with the Lilly-designated medical monitor. At a minimum, this evaluation should include physical examination and a thorough medical history, including

- symptoms
- recent illnesses, for example,
 - heart failure
 - systemic infection
 - hypotension, or
 - seizures
- recent travel
- history of concomitant medications, including over-the-counter, herbal, and dietary supplements, and
- history of alcohol drinking and other substance abuse.

Frequency of monitoring

Initially, monitoring of symptoms and hepatic biochemical tests should be done at a frequency of 1 to 3 times weekly, based on the participant's clinical condition and hepatic biochemical tests. Subsequently, the frequency of monitoring may be lowered to once every 1 to 2 weeks, if the participant's clinical condition and lab results stabilize. Monitoring of ALT, AST, ALP, and TBL should continue until levels normalize or return to approximate baseline levels.

Comprehensive hepatic evaluation

When to perform a comprehensive evaluation

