- has changes in laboratory results described in this table

If a participant with baseline results of	develops the following elevations,	then
Elevated serum ALT		
ALT <1.5× ULN	ALT to $\geq 5\times$ ULN on 2 or more consecutive blood tests	
ALT $\geq 1.5\times$ ULN	ALT $\geq 3\times$ baseline on 2 or more consecutive blood tests	
Elevated TBL		
TBL <1.5× ULN	TBL $\geq 2\times$ ULN, except for participants with Gilbert's syndrome	
TBL $\geq 1.5\times$ ULN	TBL $\geq 2\times$ baseline	
Elevated ALP		
ALP <1.5× ULN	ALP $\geq 2\times$ ULN on 2 or more consecutive blood tests	
ALP $\geq 1.5\times$ ULN	ALP $\geq 2\times$ baseline on 2 or more consecutive blood tests	

Abbreviations: ALP = alkaline phosphatase; ALT = alanine aminotransferase; CRF = case report form; TBL = total bilirubin; ULN = upper limit of normal.

Note: The interval between the 2 consecutive blood tests should be at least 2 days.

See Section 10.5 for hepatic laboratory tests.

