10.2. Appendix 2: Clinical Laboratory Tests

The tests detailed in the table here will be performed by the Lilly-designated laboratory or by the local laboratory, as specified in the table.

Local laboratory results are only required if the central laboratory results are not available in time for study intervention administration and/or response evaluation. If a local sample is required, it is important that the sample for central analysis is obtained at the same time.

Additionally, if the local laboratory results are used to make either a study intervention decision or response evaluation, the results must be recorded.

In circumstances where the Sponsor approves local laboratory testing in lieu of central laboratory testing (in the table), the local laboratory must be qualified in accordance with applicable local regulations.

Protocol-specific requirements for inclusion or exclusion of participants are detailed in Section 5 of the protocol.

Additional tests may be performed at any time during the study as determined necessary by the investigator or required by local regulations.

Investigators must document their review of the laboratory safety results.

Clinical Laboratory Tests	Comments
Hematology	Assayed by Lilly-designated laboratory
Hemoglobin	
Hematocrit	
Erythrocyte count (red blood cells)	
Mean cell volume	
Mean cell hemoglobin	
Mean cell hemoglobin concentration	
Leukocytes (WBCs - white blood cells)	
Differential	
Percent and absolute count of	
Neutrophils, segmented	
Lymphocytes	
Monocytes	
Eosinophils	
Basophils	
Platelets	
Clinical Chemistry	Assayed by Lilly-designated laboratory
Sodium	
Potassium	
Total bilirubin	
Direct bilirubin	
Alkaline phosphatase	
Alanine aminotransferase	
Aspartate aminotransferase	

Clinical Laboratory Tests	Comments
Gamma-glutamyl transferase	
Blood urea nitrogen	
Creatinine	
Uric acid	
Total protein	
Albumin	
Glucose	Fasting at baseline and Week 24
Cholesterol	
Triglycerides	
Lipid Panel	Assayed by Lilly-designated laboratory
High-density lipoprotein	
Low-density lipoprotein (LDL-C)	This value will be calculated. If triglycerides >400 mg/dL, the direct LDL will be assayed
Very-low-density lipoprotein (VLDL-C)	
Urinalysis	Assayed by Lilly-designated laboratory
Specific gravity	
pH	
Protein	
Glucose	
Ketones	
Bilirubin	
Urobilinogen	
Blood	
Nitrite	
Urine leukocyte esterase	
Microscopic examination of sediment	
Hormones (female)	
Serum pregnancy	Assayed by Lilly-designated laboratory

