Urine pregnancy	Evaluated locally
Follicle-stimulating hormone	Assayed by Lilly-designated laboratory. Performed as needed to confirm participant's postmenopausal status
Urine Chemistry	Assayed by Lilly-designated laboratory
Albumin	
Creatinine	
Calculations	Generated by Lilly-designated laboratory
Estimated glomerular filtration rate (chronic kidney disease-epidemiology)	
Urinary albumin/creatinine ratio	
Additional Testing	Assayed by Lilly-designated laboratory
Hemoglobin A1c	

10.3. Appendix 3: Adverse Events and Serious Adverse Events: Definitions and Procedures for Recording, Evaluating, Follow-Up, and Reporting

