10.5. Appendix 5: Liver Safety: Suggested Actions and Follow-Up Assessments

Hepatic evaluation testing

The Lilly-designated central laboratory must complete the analysis of all selected testing except for microbiology testing.

Local testing may be performed *in addition to central testing* when necessary for immediate participant management.

Results will be reported if a validated test or calculation is available.

Hematology		Clinical Chemistry
Hemoglobin		Total bilirubin
Hematocrit		Direct bilirubin
Erythrocytes (RBCs - red blood cells)		Alkaline phosphatase
Leukocytes (WBCs - white blood cells)		Alanine aminotransferase
Differential:		Aspartate aminotransferase
Neutrophils, segmented		Gamma-glutamyl transferase
Lymphocytes		Creatine kinase
Monocytes		Other Chemistry
Basophils		Acetaminophen
Eosinophils		Acetaminophen protein adducts
Platelets		Alkaline phosphatase isoenzymes
Cell morphology (RBC and WBC)		Ceruloplasmin
Coagulation		Copper
Prothrombin time, INR		Ethyl alcohol
Serology		Haptoglobin
Hepatitis A virus testing:		Immunoglobulin A (quantitative)
HAV total antibody		Immunoglobulin G (quantitative)
HAV IgM antibody		Immunoglobulin M (quantitative)
Hepatitis B virus testing:		Phosphatidylethanol (PEth)
Hepatitis B surface antigen		Urine Chemistry
Hepatitis B surface antibody		Drug screen
Hepatitis B core total antibody		Ethyl glucuronide
Hepatitis B core IgM antibody		Other Serology
Hepatitis B core IgG antibody		Anti-nuclear antibody
HBV DNA ^b		Anti-smooth muscle antibody ^a
		Anti-actin antibody ^c

Hematology	Clinical Chemistry
Hepatitis C virus testing:	Epstein-Barr virus testing:
HCV antibody	EBV antibody
HCV RNA ^b	EBV DNA ^b
Hepatitis D virus testing:	Cytomegalovirus testing:
HDV antibody	CMV antibody
Hepatitis E virus testing:	CMV DNA ^b
HEV IgG antibody	Herpes simplex virus testing:
HEV IgM antibody	HSV (Type 1 and 2) antibody
HEV RNA ^b	HSV (Type 1 and 2) DNA ^b
Microbiology^d	Liver kidney microsomal type 1 antibody
Culture:	
Blood	
Urine	

a Not required if anti-actin antibody is tested.

b Reflex/confirmation dependent on regulatory requirements, testing availability, or both.

c Not required if anti-smooth muscle antibody (ASMA) is tested.

d Assayed ONLY by investigator-designated local laboratory; no central testing available.

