16.1 Variables and derivations

All laboratory parameters mentioned in protocol section 10.5 will be summarized.

Quantitative laboratory measurements reported as “< X”, i.e., below limit of quantitation, or “> X”, i.e., above the upper limit of quantification, will be converted to X for quantitative summaries, but will be presented as recorded, i.e., as “< X” or “> X” in the data listings.

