16.2 Analysis

Population: SAF and PP

Stratification: Table: Add the strata as needed in case subjects with dose modification exceeding 20% based on enrolled population as per section 7.3:

- a. Subjects on 1.5 mg only
- b. Subjects on 0.75 mg only
- c. Subjects with any dose modification*

* Subjects who have received at least one dose of 1.5 mg and at least one dose of 0.75 mg

Listing: by subject, visit and each laboratory test parameter

Statistics: Summaries of all the laboratory tests will include descriptive statistics of the following:

- Actual and change from baseline (number of patients, mean, SD, median, minimum, maximum, and interquartile ranges) (for quantitative measurements)
- Frequencies and percentages (n and %) (for qualitative measurements)

All the laboratory tests will be listed separately and listing of abnormal laboratory test will be presented.

Continuous chemistry and hematology measures will be summarized as change from baseline to Week 24 using the general linear model, with the baseline value of the response variable as covariate and the estimate and 95% CI will be presented. In addition, a descriptive analysis for actual value and change from baseline will be performed

using LOCF. It will be performed using the baseline or 12-week value, if the 24-week value is missing.

17. Vital signs

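### SAP 16.1 takes its safety laboratory list from the protocol's triggered liver work-up (10.5) instead of the scheduled tests (10.2), leaving eGFR, UACR and HDL/LDL/VLDL without a specific summary plan

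*SAP*

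**What the plan says.** SAP 16.1, the variables section for safety laboratory tests, sets the scope in one sentence: "All laboratory parameters mentioned in protocol section 10.5 will be summarized".

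That protocol section is headed "10.5. Appendix 5: Liver Safety: Suggested Actions and Follow-Up Assessments". It holds a blood count, liver enzymes and bilirubin, creatine kinase, coagulation, hepatitis and other viral serology, autoantibodies, toxicology and cultures. Protocol 8.2.5 uses it under the heading "Initiating laboratory and clinical monitoring for abnormal liver laboratory test results", and the note to the last table there reads "See Section 10.5 for hepatic laboratory tests".

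For routine safety testing the protocol points elsewhere. Section 8.2.4 states: "See Appendix 2 for the list of clinical laboratory tests to be performed and the SoA for the timing and frequency". Appendix 2 is "10.2. Appendix 2: Clinical Laboratory Tests".

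SAP 16.2 then says: "Summaries of all the laboratory tests will include descriptive statistics of the following". It goes on to actual values and changes for quantitative tests and counts for qualitative tests. It adds separate listings of all tests, a listing of abnormal results, a Week 24 general linear model for continuous chemistry and hematology, and a carry-forward descriptive summary. Protocol 9.4.5 plans descriptive summaries of continuous chemistry and hematology at the SoA visits and the same kind of Week 24 model. SAP section 5 states that the protocol's methods were adopted without change.

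**The concern.** A variables section tells the programmer which parameters go into the tables. Followed literally, this one asks for summaries of serology and toxicology tests that most patients will never have. It also leaves out tests that the SoA schedules for every treated patient.

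Safety is the primary objective, and the study exists to meet a marketing-authorization condition. Patients may enter with an eGFR as low as 15 mL/min/1.73 m², and eGFR is measured before treatment and again at Week 24. If renal and lipid changes are collected but not clearly in the table plan, they may go unsummarised. If they are added after database lock, they will look post hoc.

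**Working it through.** The plan states no figure on this point, so there is none to reproduce. The check compares the two protocol lists and then asks what the other text recovers.

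**Step 1. Overlap of protocol 10.2 with protocol 10.5, by line item**

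| Group in 10.2 | Items | Also in 10.5 | Not in 10.5 |
|---|---|---|---|
| Hematology | 13 | 10 | MCV, MCH, MCHC |
| Clinical chemistry | 16 | 6 (total and direct bilirubin, ALP, ALT, AST, GGT) | sodium, potassium, urea nitrogen, creatinine, uric acid, total protein, albumin, glucose, cholesterol, triglycerides |
| Lipid panel | 3 | 0 | HDL, LDL, VLDL |
| Urinalysis | 11 | 0 | all |
| Urine chemistry | 2 | 0 | urine albumin, urine creatinine |
| Calculations | 2 | 0 | eGFR, UACR |
| HbA1c | 1 | 0 | HbA1c |
| Pregnancy tests and FSH | 3 | 0 | all |
| **Total** | **51** | **16** | **35** |

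Coverage is 16/51 = 31%. Citing 10.2 instead gives 51/51.

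**Step 2. What other text recovers from the 35**

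- Continuous chemistry and hematology (protocol 9.4.5 and SAP 16.2), reading chemistry as the 10.2 group of that name: 10 + 3 = 13 items. That leaves 35 − 13 = 22.
- HbA1c has its own analysis in SAP 19: 22 − 1 = 21. (Fasting blood glucose is likewise analysed in SAP 20.2.)
- Pregnancy tests and FSH serve eligibility and pregnancy checks and need no summary table: 21 − 3 = 18.
- Urinalysis is scheduled at screening only, so there is no on-treatment change to summarise: 18 − 11 = 7.

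The remaining 7 are HDL, LDL, VLDL, eGFR, UACR, and the urine albumin and urine creatinine from which UACR is formed. That makes five reportable results.

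**Step 3. Are those five scheduled on treatment?**

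Yes. The SoA has eGFR at screening, Week 0 and Week 24, and UACR and the lipid panel at Weeks 0 and 24. In the layout of 10.2 they sit outside both the chemistry and the hematology groups. No sentence in the SAP names them.

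**Step 4. Is the reference deliberate, or explained by renumbering?**

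A deliberate narrowing would contradict SAP section 5. The SAP is based on protocol version 1.0, which was not supplied, so renumbering cannot be ruled out completely. It is unlikely: the SAP's references to protocol 10.3 for adverse event definitions and 1.3 for the SoA both match the current numbering, and the amendment table records no renumbering.

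**The case against.** The strongest reply is that SAP 16.2 already makes the intention plain. It speaks of every laboratory test, not a subset, and lists them all. Its Week 24 model with a baseline covariate, and its carry-forward of a Week 12 value, make sense only for scheduled tests. Protocol 9.4.5 requires chemistry and hematology summaries in its own right. Table content is also fixed in a separate output-templates document, which was not available and may be correct. Laboratory values other than HbA1c and fasting glucose are not endpoints, and clinically relevant changes must be reported as adverse events. No data are lost.

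Much of this stands. A reader might infer from 16.1 that electrolytes, urea nitrogen and creatinine will go unreported, or that kidney safety as a whole has no planned summary. The documents do not support that. These analytes are in the chemistry group of protocol 10.2, and chemistry has planned descriptive summaries and a Week 24 model. Nor does the SAP restrict chemistry and hematology to the model alone. A reader might also infer that on-treatment urinalysis tables would be missing, but none are possible under the SoA. Section 10.5 is not free of urine tests either: it has a drug screen, ethyl glucuronide and a urine culture. What it lacks is routine urinalysis and UACR.

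The reply does not make the reference right. SAP 16.2 names no tests, and 16.1 is the section that defines them, so the two conflict. For eGFR, UACR and the lipoprotein fractions nothing else settles the matter, and a listing is not a summary.

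**Conclusion.** SAP 16.1 cites the wrong protocol section. It is a cross-reference error in an operative scoping sentence, with a limited consequence: five results scheduled at Weeks 0 and 24 (eGFR, UACR, HDL, LDL, VLDL) have no specific summary plan, and urinalysis lacks one for baseline only. Read literally, the sentence also calls for tables of hepatic evaluation tests that only patients with abnormal liver results would have.

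This rests on two assumptions: that chemistry in protocol 9.4.5 and SAP 16.2 means the 10.2 chemistry group, and that version 1.0 of the protocol used the same section numbers. If the output templates already include the five results, the tables may come out right, but the SAP would still disagree with them.

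**What to change.** In SAP 16.1:

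- Replace the reference to protocol section 10.5 with protocol section 10.2, at the visits in the SoA (section 1.3).
- Name eGFR, UACR and the lipid panel for summaries of actual values and change from baseline. They have no scheduled Week 12 value, so the change is baseline to Week 24 in patients with both, consistent with SAP 7.5.
- State that urinalysis is summarised at baseline only.
- Exclude pregnancy tests and FSH from the summary tables and list them, since a bare reference to 10.2 would otherwise bring them in.
- Present tests that belong only to 10.5 as listings for patients who had a triggered hepatic evaluation.

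Check the output templates against the revised text. The cost is a few lines of SAP wording and a few more tables from data already collected.

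This correction will not bring in amylase or lipase. Protocol 5.2 uses amylase, and 8.3.6 uses both, but neither appears in 10.2 or 10.5. That mismatch needs to be reconciled separately.

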16.2 Analysis

Population: SAF and PP

Stratification: Table: Add the strata as needed in case subjects with dose modification exceeding 20% based on enrolled population as per section 7.3:

- a. Subjects on 1.5 mg only
- b. Subjects on 0.75 mg only
- c. Subjects with any dose modification*

* Subjects who have received at least one dose of 1.5 mg and at least one dose of 0.75 mg

Listing: by subject, visit and each laboratory test parameter

Statistics: Summaries of all the laboratory tests will include descriptive statistics of the following:

- Actual and change from baseline (number of patients, mean, SD, median, minimum, maximum, and interquartile ranges) (for quantitative measurements)
- Frequencies and percentages (n and %) (for qualitative measurements)

All the laboratory tests will be listed separately and listing of abnormal laboratory test will be presented.

Continuous chemistry and hematology measures will be summarized as change from baseline to Week 24 using the general linear model, with the baseline value of the response variable as covariate and the estimate and 95% CI will be presented. In addition, a descriptive analysis for actual value and change from baseline will be performed

using LOCF. It will be performed using the baseline or 12-week value, if the 24-week value is missing.

17. Vital signs

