6.2 Full Analysis Set (FAS)

All patients who received at least 1 dose of study treatment and have at least 1 measurement of HbA1c after study treatment.

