6.4 Safety Analysis Set (SAF)

All patients who received at least 1 dose of study treatment.

7. General considerations

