7.2 Baseline

Baseline is defined as the last non-missing observation made prior to the first treatment administration.

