7.5 Common calculations

Change from baseline will only be calculated for patients with both baseline and post baseline values as:

$$\text{Change from baseline} = \text{postbaseline value} - \text{baseline value}$$

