8.2 Missing data

For the actual value and change from baseline, a descriptive analysis using LOCF will be performed, using the baseline or 12-week value, if the 24-week value is missing or occurred after use of rescue medication. While performing the mixed modelling with repeated measures (MMRM) Missing data will be assumed missing at random and will be accommodated by the MMRM.

If convergence is not met in the MMRM, the change in HbA1c level from baseline to Week 24 will be analysed using the general linear model and The LOCF method of missing value imputation will be used.

If none of the models converge then an analysis of covariance using LOCF imputation with similar terms as in the MMRM (except no terms that include visit) will be used in its place for body weight, fasting blood glucose, systolic blood pressure, diastolic blood pressure and pulse rate.

9. Output presentations

The templates provided in the separate output templates document describe the format and content for presentation of tables, listings, and figures (TLFs).

Summary statistics will be provided for the observed value and change from baseline will be summarized.

Unless otherwise specified, testing effect of dulaglutide on change from baseline will be conducted at a 2-sided alpha level of 0.05, and CIs will be calculated at 95%, 2-sided.

For continuous measures, summary statistics will include number of patients, mean, SD, median, minimum, maximum, and interquartile ranges for both the actual and the change from baseline measurements. Number of missing values will be specified along with this information.

For categorical measures, summary statistics will include sample size, frequency, and percentages. Number of missing values will be specified along with this information.

10. Participant disposition and withdrawal**10.1 Variables and derivations**

The trial classifications are defined as follows:

- Screening failure:

Individuals who do not meet the criteria for participation in this study (screen failure) may be rescreened after 4 weeks from the date of screen failure after discussion with the medical monitor.

- Completed trial:

A participant is considered to have completed the study if the participant has completed all periods of the study including the last visit.

- Lost to follow-up:

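### SAP 16.2 lets the pre-dose laboratory value stand in for Week 24, so treated patients with no Week 12 or Week 24 sample are tabulated with a change of exactly 0

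*SAP*

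**What the plan says.** SAP 16.2 first plans a general linear model for change to Week 24 in continuous chemistry and hematology. It then continues: "In addition, a descriptive analysis for actual value and change from baseline will be performed" by LOCF, with the rule "It will be performed using the baseline or 12-week value, if the 24-week value is missing".

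Four other statements fix what this means:

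- **Population.** The line in SAP 16.2 reads "Population: SAF and PP". SAP 6.4 defines the safety set as "All patients who received at least 1 dose of study treatment". The full analysis set in SAP 6.2 asks for more: "All patients who received at least 1 dose of study treatment and have at least 1 measurement of HbA1c after study treatment".
- **Baseline.** SAP 7.2: "Baseline is defined as the last non-missing observation made prior to the first treatment administration".
- **Change.** SAP 7.5: "Change from baseline will only be calculated for patients with both baseline and post baseline values as" post-baseline minus baseline. Protocol 9.4.1 has the same rule.
- **Sampling.** After Visit 2, the Schedule of Activities (Protocol 1.3) has hematology and chemistry only at Weeks 12 and 24.

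Protocol 9.4.5 plans descriptive statistics by visit and a general linear model for laboratory data, with no LOCF summary. LOCF in Protocol 9.4.1 is only a fallback if no repeated-measures model converges, and it does not name the baseline value. Carrying the baseline value forward is prespecified in Protocol 9.4.3, for HbA1c. SAP 8.2 repeats that rule in general terms: "using the baseline or 12-week value, if the 24-week value is missing or occurred after use of rescue medication". SAP section 5 declares no changes to the planned analyses.

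**The concern.** A patient who takes a few doses and leaves at Week 6 has chemistry from before the first dose and no scheduled sample afterwards. Under SAP 16.2 that pre-dose value is reported as the Week 24 value, and the change is baseline minus baseline. The table then counts the patient as having had no laboratory change on dulaglutide, although no scheduled sample was taken on drug.

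For an efficacy measure such as HbA1c, an imputed zero works against the drug. For a safety laboratory test it works in the drug's favour: the mean change moves towards 0 and the spread usually narrows. Safety is the primary objective of this trial, so a convention that reassures by construction should not enter a safety table unnoticed. The rule also leaves the programmer with two instructions, SAP 7.5 and SAP 16.2, that cannot both be followed for the change summary.

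**Working it through.** **Plan's own numbers (Protocol 9.6).** 250 × (1 − 0.20) = 200 treated. 200 × (1 − 0.20) = 160 at the end of the study. Both figures reproduce, and they leave 200 − 160 = 40 planned dropouts.

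**How many patients have no Week 12 or Week 24 sample.** The documents do not say when dropouts leave, so the range is 0 to 40. With even spread (assumption):

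- over the 24-week treatment period: 40 × 12/24 = 20 patients, or 20/200 = 10%;
- over 28 weeks, since completion under Protocol 4.4 includes the last visit: 40 × 12/28 ≈ 17 patients, or about 8.6%.

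**Effect on the mean.** Let k of N = 200 patients have no post-dose value, and let f = k/N. Each of the k contributes exactly 0, so

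LOCF mean = (1 − f) × mean in patients with a post-dose value.

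This compares two summaries of the same data. It needs no assumption about what the missing patients would have shown.

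**Effect on the SD.** Take the SD of real changes as 1 and their mean as d (in SD units, assumed 0.2, 0.5 or 1.0). In large samples,

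LOCF SD = √[(1 − f)(1 + f·d²)].

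| k | f | Mean kept | SD, d = 0.2 | SD, d = 0.5 | SD, d = 1.0 |
|---|---|---|---|---|---|
| 0 | 0 | 100% | 1.00 | 1.00 | 1.00 |
| 10 | 0.05 | 95% | 0.98 | 0.98 | 1.00 |
| 17 | 0.085 | 91.5% | 0.96 | 0.97 | 1.00 |
| 20 | 0.10 | 90% | 0.95 | 0.96 | 0.99 |
| 40 | 0.20 | 80% | 0.90 | 0.92 | 0.98 |

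The SD falls whenever d² < 1/(1 − f); at f = 0.10 that means d below about 1.05. For k = 20 and d = 0.5, the table would show a mean of 0.45 with n = 200, where the SAP 7.5 rule gives 0.50 with n = 180.

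**Can another sample replace the zero?** Not on the wording. The rule names only the baseline and 12-week values, and SAP 7.1 keeps unscheduled measurements out of by-visit summaries.

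**The case against.** **SAP 7.5 may govern.** On that reading a patient with no post-baseline value has no change, and the baseline is carried forward only for the actual value. No zeros then enter the change summary. This is possible, but it leaves the word baseline in the SAP 16.2 rule with no function for change, although that rule covers change explicitly. Pre-dose values would still be reported as Week 24 values. The problem becomes smaller but does not go away.

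**Only one table is affected.** This stands. SAP 16.2 also gives observed actual values and changes, full listings and a listing of abnormal tests. The per-protocol version requires completion of 24 weeks, so it is barely touched.

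**Early leavers may still be sampled.** This partly stands. Protocol 7.1 keeps patients who stop drug on the visit schedule, which lowers k. Protocol 7.2 mentions an early discontinuation visit, but the Schedule of Activities shows none and the LOCF rule would not name its value.

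A reader might also infer more than the documents support:

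- **Lipid panel, eGFR and urinary albumin/creatinine ratio.** These have no Week 12 sample, so LOCF would set every missing Week 24 value to no change, up to 40 patients. But the LOCF sentence directly follows one on chemistry and hematology, and Protocol 10.2 lists these tests as separate groups. That the LOCF covers them is not established.
- **Standard errors and confidence intervals.** The statistics listed in SAP 16.2 include the SD but no SE. SAP section 23 includes an SE by default, but only where nothing else is specified. The one confidence interval in 16.2 belongs to the general linear model, for which no LOCF is stated.
- **HbA1c.** The same rule is prespecified in Protocol 9.4.3, the full analysis set already requires a post-treatment HbA1c, and a zero change there is conservative. It is not an error in the SAP.

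**Conclusion.** The point holds for the supplementary LOCF table of continuous chemistry and hematology in the safety set. As written, SAP 16.2 assigns a change of exactly 0 to treated patients with no Week 12 or Week 24 sample, against SAP 7.5 and Protocol 9.4.1. The summary is also an addition to Protocol 9.4.5 that SAP section 5 does not declare.

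With dropout spread evenly over 24 to 28 weeks, the mean change in that table is about 9–10% closer to 0 than in patients with a post-dose value, and the SD is modestly reduced unless the mean change is about one SD or more. The limits are 0% if every dropout gives a Week 12 sample and 20% if all 40 leave before Week 12. The result rests on the planned 20% dropout, on the assumed timing, and on SAP 16.2 being applied literally.

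A reader might conclude that the trial's laboratory safety results as a whole are diluted. They are not: the observed summaries and listings are untouched, and so is the general linear model provided it runs on observed data, which SAP 16.2 does not state. The primary endpoints are adverse events and do not use this rule.

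**What to change.** In SAP 16.2:

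1. Carry forward only the post-baseline (Week 12) value when Week 24 is missing.
2. Count patients with no post-baseline value as missing and show their number, as SAP 7.5 requires.
3. State that the LOCF covers chemistry and hematology only; tests without a Week 12 sample have nothing to carry forward.
4. State that the general linear model uses observed data.

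In SAP section 5, list the laboratory LOCF summary as an addition to the protocol. Leave the HbA1c LOCF in SAP 8.2 and 19.1.2 as Protocol 9.4.3 prespecifies it, and label it as a conservative baseline-carried-forward summary for HbA1c.

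The cost is SAP wording and a slightly smaller n in the LOCF table, about 180 to 183 in place of 200 under even dropout. Trial conduct does not change. Under Protocol 9.4.1, a change that does not touch a principal feature needs no amendment, only a description and justification in the study report.
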